9.1.1. Additional Details on Recording Adverse Events on the CRF

All events detailed in the table above will be recorded on the AE page(s) of the CRF. It should be noted that the Vaccine SAE Reporting Form for reporting of SAE information is not the same as the AE page of the CRF. When the same data are collected, the forms must be completed in a consistent manner. AEs should be recorded using concise medical terminology and the same AE term should be used on both the CRF and the Vaccine SAE Reporting Form for reporting of SAE information.

9.1.2. Eliciting Adverse Event Information

The investigator is to record on the CRF all directly observed AEs and all AEs spontaneously reported by the study participant/parent(s). In addition, each study participant/parent(s) will be questioned about the occurrence of AEs in a nonleading manner.

9.1.3. Withdrawal From the Study Due to Adverse Events (see also the Participant Withdrawal Section)

Withdrawal due to AEs should be distinguished from withdrawal due to other causes, according to the definition of AE noted below, and recorded on the CRF.

When a participant withdraws from the study because of an SAE, the SAE must be recorded on the CRF and reported, as appropriate, on the Vaccine SAE Reporting Form, in accordance with the Requirements section, Section 9.1, above.

9.1.4. Time Period and Frequency for Collecting AE/SAE Information

The time period for actively eliciting and collecting AEs and SAEs ("active collection period") for each nonpregnant participant begins from the time the participant provides informed consent, which is obtained before the participant's participation in the study (ie, before undergoing any study-related procedure and/or receiving study intervention), through and including Visit 3, and from Visit 5 to Visit 7. Between Visit 3 and Visit 4, and between Visit 7 and Visit 10, only SAEs (including hospitalizations) and MAEs will be reported.

The time period for actively eliciting and collecting AEs and SAEs ("active collection period") for each maternal participant including her fetus begins from the time the maternal participant provides informed consent, which is obtained before the participant's participation in the study (ie, before undergoing any study-related procedure and/or receiving study intervention), through and including a minimum of 28 calendar days (except as indicated below) after the last administration of the study intervention.

Follow-up by the investigator continues throughout and after the active collection period and until the AE or SAE or its sequelae resolve or stabilize at a level acceptable to the investigator.

For participants who are screen failures, the active collection period ends when screen failure status is determined.

If the participant withdraws from the study and also withdraws consent for the collection of future information, the active collection period ends when consent is withdrawn.

If a participant permanently discontinues or temporarily discontinues study intervention because of an AE or SAE, the AE or SAE must be recorded on the CRF and the SAE reported using the Vaccine SAE Reporting Form.

Investigators are not obligated to actively seek AEs or SAEs after the participant has concluded study participation. However, if the investigator learns of any SAE, including a death, at any time after a participant has completed the study, and he/she considers the event to be reasonably related to the study intervention, the investigator must promptly report the SAE to Pfizer using the Vaccine SAE Reporting Form.

9.1.4.1. Stage 1

The investigator and site staff will ensure the active elicitation and collection of AEs and SAEs through Visit 3. At Month 6 (Visit 4), the participant will be contacted by telephone to inquire about MAEs and SAEs, including hospitalizations since Visit 3. For participants receiving the booster vaccination, site staff will ensure the active elicitation and collection of AEs and SAEs from Visit 5 to Visit 7. At Visit 8 (3-month booster vaccination follow-up visit), Visit 9 (6-month booster vaccination follow-up visit), and Visit 10 (blood draw follow-up visit), MAEs and SAEs (including hospitalizations) since the previous visit will be recorded.

Immediate AEs will be reported as detailed in Section 8.8.2.

9.1.4.2. Stages 2 and 3 – Maternal Participants

In this study, the investigator and site staff will ensure the active elicitation and collection of AEs and SAEs through Visit 3. At 1 week following delivery (Visit 5), the participant will be contacted by telephone to inquire about MAEs and SAEs, including hospitalizations, since Visit 3. At all subsequent visits (Visits 6, 7, 8, and 9), only MAEs and SAEs, including hospitalizations, will be reported.

Immediate AEs will be reported as detailed in Section 8.8.2.

In addition, AEs occurring up to 48 hours after the Visit 4, Visit 6, and Visit 9 blood draws that are related to study procedures must be reported in the CRF.

9.1.4.3. Stages 2 and 3 - Infant Participants

The investigator and site staff will ensure the active elicitation and collection of AEs and SAEs from birth (Visit 1) through Visit 3. At subsequent visits (Visit 4, Visit 5, Visit 6, and Visit 7), only AEs of special interest, MAEs, and SAEs, including hospitalizations, will be reported.

In addition, AEs occurring up to 48 hours after the Visit 4, 5, and 7 blood draws that are related to study procedures must be reported in the CRF. In addition, AEs occurring up to 48 hours after the Visit 4 CCI that are related to study procedures must be reported in the CRF.

Refer to Table 8 for a summary of AE/SAE collection.

Table 8. Time Period for Collecting AE/SAE Information

Safety Event	Stage 1	Stages 2 and 3 Maternal Participant	Stages 2 and 3 Infant Participant
Nonserious AE	Consent – Visit 3 Visit 5 – Visit 7	Consent – Visit 3	Visit 1 (birth) – Visit 3
SAE	Consent – Visit 4 Visit 5 – Visit 10	Consent – Visit 9	Visit 1 – Visit 7
MAE	Consent – Visit 4 Visit 5 – Visit 10	Consent – Visit 9	Visit 1 – Visit 7
AE of special interest	N/A	N/A	Visit 1 – Visit 7
Immediate AE	Within 30 minutes of IP administration	Within 30 minutes of IP administration	N/A
AE related to study procedure	Not applicable ^a	Visit 4, Visit 6, and Visit 9 (up to 48 hours after blood draw)	Visit 4, Visit 5, and Visit 7 (up to 48 hours after blood draw/swab collection)

Abbreviations: IP = investigational product; MAE = medically attended adverse event; N/A = not applicable.

9.1.4.4. Reporting SAEs to Pfizer Safety

All SAEs occurring in a participant during the active collection period as described in Section 9.1.4 are reported to Pfizer Safety on the Vaccine SAE Reporting Form, immediately upon awareness and under no circumstance should this exceed 24 hours, and the Exposure During Pregnancy Supplemental Form (Stage 1 participants only), if applicable. The investigator will submit any updated SAE data to the sponsor within 24 hours of it being available.

a. Study procedures will only be performed in Stage 1 during the standard AE/SAE reporting period, thus AEs related to study procedures are not applicable. Therefore, during Stage 1, these events will be reported as per standard AE reporting requirements detailed in Section 9.1.4.1.

If the outcome of the pregnancy meets the criteria for an SAE (ie, ectopic pregnancy, spontaneous abortion, including miscarriage and missed abortion, intrauterine fetal demise, neonatal death [defined as those deaths that occur within 1 month of birth], or congenital anomaly [defined as structural or functional anomalies (eg, metabolic disorders) that occur during intrauterine life and can be identified prenatally, at birth or later in life]). These SAEs can occur in a live-born baby, a terminated fetus, an intrauterine fetal demise, or a neonatal death; the investigator should follow the procedures for reporting SAEs and record this information in the CRF. In addition, infant deaths after 1 month of age should be reported as SAEs and recorded in the CRF.

Further follow-up may be requested by the sponsor and will be handled on a case-by-case basis (eg, follow-up on preterm infant participants to identify developmental delays).

SAEs occurring in a participant after the active collection period has ended are reported to Pfizer Safety if the investigator becomes aware of them; at a minimum, all SAEs that the investigator believes have at least a reasonable possibility of being related to investigational product must be reported to Pfizer Safety.

The same is applied for those SAEs after the active collection period has ended should they occur to the fetus. In addition, infant deaths that occur after 12 months of age should be reported as SAEs when the investigator believes the death has at least a reasonable possibility of being related to investigational product.

Follow-up by the investigator continues throughout and after the active collection period and until the event or its sequelae resolve or stabilize at a level acceptable to the investigator, and Pfizer concurs with that assessment.

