7.1.8. Visit 7 – 1-Month Booster Vaccination Follow-Up Visit (28-42 Days After Visit 6)

- Ensure that the participant continues to be eligible for the study and meets none of the participant withdrawal criteria as described in Section 7.5.
- Verify understanding of and compliance with protocol requirements for contraception.
- Collect a blood sample of approximately 140 mL.
- Review the participant's e-diary data and collect the e-diary. Collect stop dates of any e-diary events ongoing on the last day that the e-diary was completed and record stop dates in the CRF.
- Complete the participant's source documents.
- Record nonstudy vaccinations and concomitant medications as described in Section 6.10.3.
- Record AEs as described in Section 8.8 and Section 9.
- The investigator or an authorized designee completes the CRF.

7.1.9. Visit 8 – 3-Month Booster Vaccination Follow-Up Visit (84-126 Days After Visit 6)

- Ensure that the participant continues to be eligible for the study and meets none of the
 participant withdrawal criteria as described in Section 7.5.
- Verify understanding of and compliance with protocol requirements for contraception.
- Collect a blood sample of approximately 140 mL.
- Complete the participant's source documents.
- Record concomitant medications as described in Section 6.10.3. Only concomitant medication taken to treat an AE will be recorded in the CRF.
- Record AEs as described in Section 8.8 and Section 9.
- The investigator or an authorized designee completes the CRF.

7.1.10. Visit 9 – 6-Month Booster Vaccination Follow-Up Visit (160-200 Days After Visit 6)

- Ensure that the participant continues to be eligible for the study and meets none of the participant withdrawal criteria as described in Section 7.5.
- Verify understanding of and compliance with protocol requirements for contraception.
- Collect a blood sample of approximately 140 mL.
- Complete the participant's source documents.
- Record concomitant medications as described in Section 6.10.3. Only concomitant medications taken to treat an AE will be recorded in the CRF.
- Record AEs as described in Section 8.8 and Section 9.
- The investigator or an authorized designee completes the CRF.

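### Table 8 footnote a leaves Stage 1 booster Visits 8, 9 and 10 without active collection of nonserious procedure-related AEs; secondarily, the stated length of booster MAE/SAE follow-up is loose at its lower end

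*Protocol*

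**What the plan says.** Protocol Table 8 sets the Stage 1 nonserious-AE window as consent to Visit 3 and Visit 5 to Visit 7. SAEs and MAEs run to Visit 4 and then from Visit 5 to Visit 10. The procedure-related row is not applicable for Stage 1. Footnote a gives the reason: "Study procedures will only be performed in Stage 1 during the standard AE/SAE reporting period, thus AEs related to study procedures are not applicable". It continues: "Therefore, during Stage 1, these events will be reported as per standard AE reporting requirements detailed in Section 9.1.4.1".

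Section 9.1.4 states that "between Visit 7 and Visit 10, only SAEs (including hospitalizations) and MAEs will be reported". Section 9.1.4.1 says the same for Visits 8, 9 and 10: "MAEs and SAEs (including hospitalizations) since the previous visit will be recorded". The Stage 1 schedule of activities marks general AE recording at Visits 0 to 3 and 5 to 7 only.

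Blood is drawn after that. Sections 7.1.9 and 7.1.10 (Visits 8 and 9) each say "Collect a blood sample of approximately 140 mL", and Section 7.1.11 (Visit 10) asks for about 125 mL.

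The other cohorts have a specific rule. For mothers, Section 9.1.4.2 requires reporting of "AEs occurring up to 48 hours after the Visit 4, Visit 6, and Visit 9 blood draws that are related to study procedures". For infants, Section 9.1.4.3 covers "AEs occurring up to 48 hours after the Visit 4, 5, and 7 blood draws that are related to study procedures".

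On follow-up length, Protocol 3.1.2 and SAP 3.1.1 and 6.1.1.4 give the booster MAE/SAE endpoint as approximately 7 to 12 months. Protocol 4.2 ties this to Visit 10.

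**The concern.** The reason given in footnote a holds for the primary series, where the last draw is at Visit 3 and Visit 4 is a telephone contact. It does not carry over to the booster phase, where three large draws follow the end of nonserious-AE collection. Section 9.1.4.1, to which the footnote sends the site, contains no instruction to ask about nonserious reactions to those draws.

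What is at stake is the capture of procedure-related harm in healthy volunteers, much of whose blood is taken to develop an assay reference standard. A Stage 1 site that follows Table 8 will not ask about the 48 hours after these draws; a maternal or infant site will.

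The follow-up label raises a smaller point. Crude MAE/SAE proportions are planned without any summary of how long each woman was followed, and the visit windows allow that time to differ considerably.

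**Working it through.** **1. Procedure-related AEs: the provisions side by side**

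| | Stage 1 booster | Maternal | Infant |
|---|---|---|---|
| Nonserious AEs end | Visit 7 | Visit 3 | Visit 3 |
| SAEs and MAEs end | Visit 10 | Visit 9 | Visit 7 |
| Later draws | Visits 8, 9, 10 | Visits 4, 6, 9 | Visits 4, 5, 7 |
| Approximate volume per draw | 140, 140, 125 mL | 15 mL | 5 mL |
| 48-hour procedure-AE rule | none | yes | yes |

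The infant draws at Visits 5 and 7 are not required for US and UK Stage 3 infants. The infant comparison is in absolute volume only; the mothers are the closer comparison, being adult women.

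- Volume after nonserious-AE collection ends: 140 + 140 + 125 = 405 mL per woman.
- Visit 7 is day 28 to 42 after the booster and Visit 8 is day 84 to 126. The first uncovered draw is therefore at least 84 − 42 = 42 days after nonserious-AE collection ends.
- Visit 10 falls between 174 − 42 = 132 and 384 − 28 = 356 days after Visit 7 (the 174 and 384 are derived in part 2).
- Upper bound: 66 women × 3 draws = 198 draws. The number is lower in practice, because the booster and Visit 10 each need separate consent.

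If the footnote's reporting period is read as the SAE/MAE window to Visit 10, its premise becomes true, but its conclusion does not follow. The maternal and infant columns also carry SAE and MAE collection to the last visit and still have the 48-hour rule. Even on that reading, the 48 hours after the Visit 10 draw lie beyond the window, which ends at Visit 10 itself.

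**2. Length of booster MAE/SAE follow-up**

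Inputs: Visit 9 is 160 to 200 days after the booster (7.1.10); Visit 10 is 14 to 184 days after Visit 9 (7.1.11). One month = 30.4375 days, so 7 months = 213 days (rounded).

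First, the plan's own figure. With Visit 9 at a nominal day 180:

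- 180 + 14 = 194 days = 6.4 months
- 180 + 184 = 364 days = 12.0 months

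The 12 is reproduced but the 7 is not. With Visit 9 on day 200, the lower end is 214 days = 7.0 months, but the upper end becomes 384 days = 12.6 months. No single Visit 9 day gives both 7 and 12.

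The full permitted range:

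- Minimum: 160 + 14 = 174 days = 5.7 months, which is 213 − 174 = 39 days short of 7 months.
- Maximum: 200 + 184 = 384 days = 12.6 months.
- Span: 384 − 174 = 210 days; ratio 384 / 174 = 2.2.

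The gap from Visit 9 to Visit 10 needed to reach day 213 is 53 days if Visit 9 is on day 160, 33 days if on day 180 and 15 days if on day 198. From day 199 the 14-day minimum is enough, so no shortfall can occur.

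The choice of month does not change the conclusion. With 30-day months the range is 5.8 to 12.8 months; with 28-day months it is 6.2 to 13.7.

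**The case against.** Several routes still capture events at these visits. Sections 7.1.9 to 7.1.11 each tell the site to record AEs as Sections 8.8 and 9 describe, and to record medication taken to treat an AE. The table in Section 9.1 has all Stage 1 nonserious AEs recorded on the CRF. Sections 9.1.2 and 9.1.4.5 cover events that the investigator observes or the participant volunteers. SAEs and MAEs are collected at all three visits. All of this stands and makes the gap narrow. It does not close it: Section 8.8.1 ties questioning to the active collection period, and Sections 9.1.4 and 9.1.4.1 confine these visits to MAEs and SAEs.

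A reader might infer that the gap distorts the SAP 6.1.1.4 tabulation of all AEs through Visit 10, or that the reader of that table could not tell when nonserious collection stopped. The documents do not support either inference. SAP 3.6.1 refers AE reporting to Protocol Table 8, which states the window. The same layout is planned for the Stage 1 primary series, mothers (SAP 6.1.2.5) and infants (SAP 6.1.3.3), so it does not arise from the missing procedure-AE rule.

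On follow-up length, every statement of the endpoint is approximate, and collection is fixed operationally at Visit 10. The 39-day shortfall needs both windows at their minimum. This also stands: the label is loose, but the endpoint is not wrong. Nor would it be right to present 174 to 384 days as every woman's follow-up. Visit 10 requires its own consent, and women who do not attend may end follow-up around Visit 9.

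**Conclusion.** Footnote a is wrong for the Stage 1 booster phase. Active collection is missing for nonserious, non-medically-attended reactions to the draws at Visits 8, 9 and 10 that are neither observed nor volunteered. The documents give no basis for estimating how many such events there would be; the bound is 66 women with three draws each. The label of about 7 to 12 months is a secondary wording point, loose by up to 39 days at the lower end; its approximate form covers the upper end.

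Both parts are minor. A reader might infer that a primary endpoint is compromised, but the 1-month AE endpoint ends before these draws, and MAEs and SAEs are collected through Visit 10. The booster is one open-label group and all analyses are descriptive, so no endpoint, comparison or decision is affected.

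The conclusion rests on Table 8 and Section 9.1.4 meaning what they say about the nonserious window, and on the visit windows as written. Actual visit dates may be less extreme.

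**What to change.** - **Procedure-related AEs.** Reconcile Table 8, footnote a and Section 9.1.4.1 with the visit schedule by applying the existing 48-hour procedure-AE collection to Stage 1 Visits 8, 9 and 10. For Visit 10, the mechanism that sites use after the last maternal and infant draws would serve. If these visits are complete, state the gap as a limitation in the CSR and list any such events that were recorded. SAP Table 2 footnote a already describes the booster return in the past tense, so this may be the applicable route.
- **Follow-up length.** In Protocol 3.1.2 and SAP 3.1.1 and 6.1.1.4, describe booster MAE/SAE follow-up as through Visit 10 (174 to 384 days permitted by the windows) or last contact. Report median, minimum and maximum follow-up days beside the booster MAE/SAE proportion.
- **Optional, all cohorts.** Footnote the long-term tables of all AEs with the nonserious-AE collection window.

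The cost is a few wording corrections, one follow-up-time row from dates already collected and, if the visits are still open, one short enquiry after each draw. The endpoint is not redefined.

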9.1.4.5. Recording Nonserious AEs and SAEs on the CRF

All AEs/SAEs occurring in a participant during the active collection period, which begins after obtaining informed consent as described in Section 9.1.4, will be recorded on the AE section of the CRF.

The investigator is to record on the CRF all directly observed, and all spontaneously reported AEs and SAEs reported by the participant.

The investigator obtains general information on the pregnancy and its outcome for all study participants. The investigator will follow the pregnancy until completion (or until pregnancy termination). In the case of a live birth, the structural integrity of the neonate can be assessed at the time of birth. In the event of a termination, the reason(s) for termination should be specified and, if clinically possible, the structural integrity of the terminated fetus should be assessed by gross visual inspection (unless preprocedure test findings are conclusive for a congenital anomaly and the findings are reported).

If the outcome of the pregnancy meets the criteria for an SAE (ie, ectopic pregnancy, spontaneous abortion, including miscarriage and missed abortion, intrauterine fetal demise, neonatal death [defined as those deaths that occur within 1 month of birth], or congenital anomaly [in a live-born baby, a terminated fetus, an intrauterine fetal demise, or a neonatal death]), the investigator should record this information in the CRF. In addition, infant deaths after 1 month of age should be recorded in the CRF as SAEs.

9.1.5. Follow-up of AEs and SAEs

After the initial AE or SAE report, the investigator is required to proactively follow each participant at subsequent visits/contacts. For each event, the investigator must pursue and obtain adequate information until resolution, stabilization, the event is otherwise explained, or the participant is lost to follow-up (as defined in Section 7.5.1).

In general, follow-up information will include a description of the event in sufficient detail to allow for a complete medical assessment of the case and independent determination of possible causality. Any information relevant to the event, such as concomitant medications and illnesses, must be provided. In the case of a participant death, a summary of available autopsy findings must be submitted as soon as possible to Pfizer Safety.

9.1.6. Causality Assessment

The investigator's assessment of causality must be provided for all AEs (serious and nonserious); the investigator must record the causal relationship on the CRF, and report such an assessment in accordance with the SAE reporting requirements, if applicable. An investigator's causality assessment is the determination of whether there exists a reasonable possibility that the investigational product caused or contributed to an AE; generally, the facts (evidence) or arguments to suggest a causal relationship should be provided. If the investigator does not know whether or not the investigational product caused the event, then the event will be handled as "related to investigational product" for reporting purposes, as defined by the sponsor. If the investigator's causality assessment is "unknown but not related" to investigational product, this should be clearly documented on study records.

In addition, if the investigator determines that an SAE is associated with study procedures, the investigator must record this causal relationship in the source documents and CRF, and report such an assessment in the dedicated section of the Vaccine SAE Reporting Form and in accordance with the SAE reporting requirements.

